**3.2.4.10 3D Imaging of the Chin region**

The change in topography of the chin region from Baseline will be assessed by 3D imaging to 3 and 12 months after last treatment. Assessments may include, but will not be limited to, Pogonion Projection, Total Volume Change, Positive Volume Change, and Negative Volume Change.

Confidential

Statistical Analysis Plan Version #1.0

Page 17 of 63

Version: 1.0

Effective

Galderma

Protocol number: 43USCH2208

Protocol V4.0

CCI

**3.2.5.2 Sensory tests**

The sensory tests will be performed at screening to confirm eligibility. A baseline value of sensation, evaluating the chin and lower lip, will be obtained and new assessments will be done at all physical visits thereafter. A study staff member who is qualified by training and experience to perform safety assessments will score sensation as “Normal” or “Abnormal.”

Chin and lower lip sensation will be tested using two methods: the monofilament test and the cotton wisp test.

**3.2.5.3 Functionality tests**

The functionality tests will be performed at screening to confirm eligibility. A baseline value of lip, and lip and chin movement will be obtained, and new assessments will be done at all physical visits thereafter. A study staff member who is qualified by training and experience to perform safety assessments will score lip movement and lip and chin function as “Normal” or “Abnormal.” After receiving treatment, any subject with abnormal ratings should be assessed by the Investigator for confirmation of any potential AE.

**3.2.5.4 Assessment of palpability**

Palpability will be assessed at screening, baseline and at each physical follow-up visit, prior to treatment. A study staff member who is qualified, by training and experience, to perform safety assessments will palpate the chin for detection of any unexpected feeling such as lumpiness, mass, non-uniform density, or unexpected aggregation of product. The study products are generally palpable (i.e., can be felt under the skin) and have uniform density. Any unexpected feel of the study product upon palpation of the chin will be assessed as “Abnormal”. Any abnormality should be assessed by the investigator for confirmation of any potential AE, including a description of the localization, feel and approximate size.

**3.2.5.5 Changes in hair growth**

The Treating Investigator will ask if the subject has noticed any changes in hair growth (e.g., loss or growth) in the treated area at physical follow-up visits after baseline. Clinically significant changes in hair growth, as determined by the Treating Investigator, will be reported as an AE.

**3.2.5.6 Visual Function Assessment**

Three visual function assessments will be performed at screening, baseline and at all physical follow-up visits. At the treatment visits, the visual function assessment tests will be performed prior to and approximately 30 minutes post injection of the study product.

|   |  |                                   |
|---|--|-----------------------------------|
| 
GALDERMA
<small>EST. 1981</small>
 | 
Title
43USCH2208 Statistical Analysis Plan (SAP)
 | 
Doc id
MA-60980
 |
|---|--|-----------------------------------|

Effective date: 2024-05-29 18:37

Effective

Version: 1.0

Galderma

Protocol number: 43USCH2208

Protocol V4.0

The sections below provide descriptions of the visual function assessments that will be performed.

#### 3.2.5.6.1 Snellen Visual Acuity

A Snellen eye chart will be used to objectively assess visual acuity for distance vision. Visual acuity will be conducted using the subject's best distance correction (e.g., contacts or eyeglasses) at a distance of 6 feet from the chart. Each eye will be measured separately by either using an occluder or having the subject cover each eye. The subject will be asked to start reading the letters at the top of the chart working their way to the bottom. The smallest row of letters that the subject can read will indicate their visual acuity listed on the chart. Any subject requiring vision acuity correction must be assessed using the prescribed correction (e.g., contacts or eyeglasses).

Unacceptable vision for a subject to be eligible for enrollment would be an absolute score on the Snellen eye chart 20/50 or worse in one or both eyes.

A 1+ worsening line change in Snellen Visual Acuity (VA) is when a subject moves up at least one line of letters on the Snellen Eye Chart (Figure 1). For example, if a subject's VA at baseline is 20/40 for the left and right eyes and then at Visit 1d is 20/70 for the left eye and 20/50 in the right eye, the subject experienced a 2-line worsening for the left eye and a 1-line worsening in the right eye.

Figure 1: Snellen Eye Chart

Galderma

Protocol number: 43USCH2208

Protocol V4.0

Given that VA is assessed at every study visit (pre-and-post treatment for applicable visits), there are many ways to assess a 1+ worsening line change:

- Acute worsening – A 1+ worsening line change between the pre-treatment and post-treatment VA, for visits where an injection is given.
- Compared to Previous visit – A 1+ worsening line change between the current visit VA and the previous visit VA (e.g., Visit 4 VA compared to Visit 3 VA). If the 'previous' visit has both pre-and-post treatment VA values, the post-treatment VA will be used; if the 'current' visit has both pre-and-post treatment VA values, both VAs will be compared to the 'previous' visit VA.
- Change from Baseline – A 1+ worsening line change between a post-baseline visit VA and Baseline (pre-treatment) VA. For post-baseline visits with both pre-and-post treatment VA, both will be compared to the Baseline (pre-treatment) VA.

The Snellen chart provided to sites for use in this study is 6ft. If a subject uses a different distance Snellen chart and their scores from the non-6ft Snellen chart match values found on the 6ft Snellen chart, then the 6ft Snellen chart equivalent will be used, and the subject will continue the study using the 6ft Snellen chart. For example, if a subject using a non-6ft Snellen chart scores values of 20/20, 20/25, 20/30, 20/40, 20/50, 20/70, 20/100, or 20/200 (all of which are found on the 6ft Snellen chart), then the subject's Snellen scores will remain the same, but the subject will proceed with the study using the 6ft Snellen chart.

On the other hand, if a subject uses a different distance Snellen chart and their scores from the non-6ft Snellen chart *do not consistently* match values found on the 6ft Snellen chart, then the subject will continue using the non-6ft Snellen chart for the duration of the study for safety purposes, and their observed Snellen values will remain the same in the data and data listings. In outputs presenting Snellen line changes, the line change calculation using the subject's non-6ft Snellen chart will be performed to determine the number of line changes separately for each eye (left and right). For example, if at any point a subject using a non-6ft Snellen chart scores values of 20/16, 20/60, 20/80, etc., then the data and data listings will present these non-6ft values. In the Snellen line change outputs, the type of Snellen chart will be considered when calculating line changes.

At the time this SAP was drafted, one site ([name] site 8651) was identified as having used a non-6ft Snellen chart. For subjects at site 8651 with Snellen chart scores that do not match the scores on the 6-ft Snellen chart (i.e. any score other than 20/20, 20/25, 20/30, 20/40, 20/50, 20/70, 20/100, or 20/200), the following [name] 10-ft Snellen chart will be considered when calculating line changes.

|  |  |                                   |
|--|--|-----------------------------------|
| 
GALDERMA
<small>© 1991</small>
 | 
Title
43USCH2208 Statistical Analysis Plan (SAP)
 | 
Doc id
MA-60980
 |
|--|--|-----------------------------------|

Galderma

Protocol number: 43USCH2208

Protocol V4.0

Figure 2: [name] 8651 10ft Snellen Chart

[figure not shown]

#### 3.2.5.6.2 Extraocular Muscle Function

Extraocular muscle function testing examines the function of the eye muscles. This test observes the movement of the eyes in six specific directions to evaluate weakness or other problems in the extraocular muscles. The subject will be asked to sit or stand with his/her head up and looking straight ahead. The assessor will hold a pen or other object approximately 16 inches in front of the subject's face. The assessor will then move the object in several directions and ask the subject to follow it with their eyes, without moving their head. The result shall be reported as "normal" or "abnormal" for each eye.

#### 3.2.5.6.3 Confrontation Visual Field

The confrontation visual field test will be used to assess the subject's peripheral vision. The examiner will sit facing the subject, about 3 to 4 feet away from the subject and ask the subject to fix their gaze on the examiner's eye. The examiner will hold their arms straight out to the side and bring their hands into the subject's visual field from the sides in each quadrant. The subject will signal as soon as the hand is seen. Each eye will be recorded as normal or abnormal.

Confidential

Statistical Analysis Plan Version #1.0

Page 21 of 63

Effective date: 2024-05-29 18:37

Effective

Version: 1.0

[figure not shown]

Effective date: 2024-05-29 18:37

Galderma

Protocol number: 43USCH2208

Protocol V4.0

## 4 General Analysis Conventions

Data for all subjects in the clinical database will be included in the data listings and sorted by treatment and subject. Calculated (derived) variables will be included in listings when appropriate. All summaries, statistical analyses, and individual subject data listings will be completed using Version 9.4 or later of SAS software (SAS Institute, Inc., Cary, North Carolina). A list of proposed statistical tables and data listings will be provided in a separate document. Any changes from the SAP will be detailed in the Clinical Study Report.

Unless otherwise specified, summary tables will be presented with different columns for each treatment (Restylane Lyft with Lidocaine or Juvéderm Voluma). An additional column for overall summaries will be presented for non-efficacy endpoints. Continuous endpoints will be summarized using the number of subjects (n), mean, median, SD, minimum and maximum values. Categorical endpoints will be presented in frequency tables with number and percentage of observations for each level.

Unless otherwise specified, confidence intervals (CIs) will be two-tailed and constructed at a confidence level of 95%, statistical tests will be performed at a significance level of 5%, and p-values will be two-sided.

Study days will be calculated relative to the first injection of study drug. Day 1 will be the first day of study drug administration in the study, and the day prior to the first dose of study drug administration will be Day -1. There will be no Day 0.

Adverse events, medical history, prior dermatological procedures and implant history, and concomitant procedures/treatments data will be coded using Medical Dictionary for Regulatory Activities (MedDRA) Version 25.1. Concomitant medications, procedural anesthetics and vaccines data will be coded using the World Health Organization (WHO) Drug Dictionary (Global B3/September 2022).

### 4.1 Study Visits

The study visits are illustrated in [Section 16.1 Study Flow Chart](#) and [Section 16.2 Schedule of Events](#).

Version: 1.0

Effective

Galderma

Protocol number: 43USCH2208

Protocol V4.0

## 4.2 Visit Windows

Study visits are expected to occur according to the protocol schedule. All data will be tabulated per the evaluation visit as recorded on the eCRF even if the assessment is outside of the visit window. In data listings, the relative study day of all dates on or after Baseline will be presented. There will not be any windowing for unscheduled visits in the analysis, and unscheduled visits will not be included in any analyses, unless used for Baseline determination. Unscheduled visits, if any, will be presented in listings only.

Analysis visit values will be generated using the raw VISIT values for use in tables. See Table below:

**Table 6: AVISIT and VISIT Values**

| Visit (VISIT)  | Presentation in Tables (AVISIT)            | Presentation in Listings |
|--|--|--------------------------|
| Visit 1a Screening Day -21 to Day 1                            | Visit 1a (Screening) {or Baseline}         | Visit 1a                 |
| Visit 1b Baseline/Tx Day 1                                     | Visit 1b (Baseline) {or Baseline}          | Visit 1b                 |
| Visit 2 (TC) 72 hrs after Baseline (+/- 24 hrs)                | Visit 2 (Hour 72 after Treatment)          | Visit 2                  |
| Visit 2a 14 days after Baseline (+ 7 days)                     | Visit 2a (Day 14 after Treatment)          | Visit 2a                 |
| Visit 3 1 month after Baseline (+ 7 days)                      | Visit 3 (Month 1 after Treatment)          | Visit 3                  |
| Visit 3a (TC) 72 hrs after Optional Touch Up (+/- 24 hrs)      | Visit 3a (Hour 72 after Optional Touch-up) | Visit 3a                 |
| Visit 3b 14 days after Optional Touch Up (+ 7 days)            | Visit 3b (Day 14 after Optional Touch-up)  | Visit 3b                 |
| Visit 3c 1 month after Optional Touch Up (+ 7 days)            | Visit 3c (Month 1 after Optional Touch-up) | Visit 3c                 |
| Visit 4 Follow-up 3 Months after Last Treatment (+/- 14 days)  | Visit 4 (Month 3 after Last Treatment)     | Visit 4                  |
| Visit 5 Follow-up 6 Months after Last Treatment (+/- 14 days)  | Visit 5 (Month 6 after Last Treatment)     | Visit 5                  |
| Visit 6 Follow-up 9 Months after Last Treatment (+/- 14 days)  | Visit 6 (Month 9 after Last Treatment)     | Visit 6                  |
| Visit 7 Follow-up 12 Months after Last Treatment (+/- 14 days) | Visit 7 (Month 12 after Last Treatment)    | Visit 7                  |

## 4.3 Study Duration

First subject first visit (FSFV) to last subject last visit (LSLV): estimated to approximately 18 months including 4 months enrollment period. Duration for each Subject will be up to 14 months, including:

Confidential

Statistical Analysis Plan Version #1.0

Page 23 of 63

Galderma

Protocol number: 43USCH2208

Protocol V4.0

- Up to 21 days screening.
- Treatment at Baseline (Day 1) and optional touch-up at 1 month.
- Data collection and safety follow-up visits at 1, 3, 6, 9 and 12 months after last treatment as well as 14 days after each treatment.

One month is defined as 4 weeks in the study and 4 weeks is defined as 28 days.

#### 4.4 Baseline Definition

Baseline will be the last assessment prior to the injection of study drug unless otherwise indicated. The Screening Visit 1 (Day -21 to Day 1) will be considered the visit prior to injection of study drug. Because the Screening visit and Baseline visit (Day 1) may be performed on the same day, the Screening visit can also be Day 1.

For all analyses, Baseline will be defined as the most recent measurement prior to the first administration of study product, including unscheduled visits conducted prior to study treatment. The change from Baseline ( $\Delta$ ) will be defined as

$$\Delta = \text{Visit } X \text{ Assessment Value} - \text{Baseline Assessment Value}$$

and will be summarized using the same descriptive statistics as other continuous endpoints.

In change from baseline analyses that treat the response as ordinal, the  $\Delta$  representing change from baseline will be treated as a categorical variable.

#### 4.5 Injection Timepoint Definition

##### 4.5.1 Injection Timepoint for PPD Study Drug Exposure

PPD

PPD Timepoint will refer to the two following periods of the study:

- Initial Treatment – At or in the 28 days following Baseline injection, prior to touch-up treatment.
- Touch-up Treatment – If subject received a touch-up treatment at Month 1, at or in the 28 days following optional Month 1 touch-up injection.

##### 4.5.2 Injection Timepoint for Adverse Events

For adverse events summaries, Injection timepoint will refer to the following periods of the study:

- Initial Treatment: at or after Baseline injection until optional touch-up treatment or end of study (EOS), whichever comes first. All adverse events for subjects who did not receive optional touch-up treatment will be included in this injection timepoint.

Galderma

Protocol number: 43USCH2208

Protocol V4.0

- Initial Treatment + Touch-up: at or after optional touch-up treatment until end of study (EOS). Subjects who did not receive optional touch-up treatment will not have adverse events included in this injection timepoint.

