### 3.2 Overall Design

This is a prospective, randomized, evaluator-blinded, parallel group, comparator-controlled, multicenter study in the US to evaluate the safety and effectiveness of Restylane Lyft with Lidocaine for augmentation of the chin region to improve the chin profile. The chin region is comprised of the anatomical areas of the pogonion, menton, and pre-jowl sulcus. Before the study starts, a randomization list will be prepared under the supervision of a designated biostatistician from the Sponsor.

Injection technique is at the Treating Investigator's discretion with needle only or a combination of needle and cannula. Restylane Lyft with Lidocaine and the comparator-

Version: 1.0

Effective

Galderma

Protocol number: 43USCH2208

Protocol V4.0

control will be administered by needle in the pogonion. The mentum and pre-jowl sulci may be injected by needle or cannula.

At least 35 subjects will be Fitzpatrick skin type (FST) IV through VI, this includes at least 18 subjects with FST V – VI, where at least 9 subjects will be FST V and at least 9 subjects will be FST VI.

After providing informed consent, eligible subjects randomized to receive either Restylane Lyft with Lidocaine or a comparator-control will be injected by the Treating Investigator at Baseline (Day 1). A follow-up telephone call should be made 72 hours after treatment and a follow-up visit should be scheduled after 14 days.

Optional touch-up treatment may be administered 1 month (4 weeks) after initial treatment, if deemed necessary by the Treating Investigator and the subject to obtain optimal aesthetic improvement. If optional touch-up is performed, a 72-hour follow-up telephone call, a follow-up visit at 14 days, and a follow-up visit at 1 month should be scheduled.

Appropriate injection volume for the chin area will be determined by the Treating Investigator but is not to exceed a maximum total volume of 4.0 mL for initial and touch-up treatments combined. Injection in the pogonion is only permitted with a needle. Both needle and cannula are permitted for injection in the other treatment areas.

Investigator blinding will be accomplished by using a Treating Investigator to administer the treatments and a Blinded Evaluator, to whom randomization and treatment are concealed, to conduct the blinded assessments. Safety assessments will be performed by non-blinded personnel.

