Effectiveness and safety data will be collected for up to 12 months (48 weeks) after last treatment including physical follow-up visits at 1, 3, 6, 9 and 12 months as well as 14 days after each treatment. A subject will be involved in the study for up to 14 months, including a 21-day screening period.

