**10.2 Adverse Events**

Adverse Event reporting on each subject will start once a subject is enrolled in the study. All other events that occur after the subject signs the ICF but before enrollment will be recorded in the subject's medical history. The reporting shall continue during each follow-up visit (including telephone contacts and extra visits between planned visits) until the last scheduled visit in the study.

All AEs reported will be listed, documenting the verbatim term, MedDRA Preferred Term (PT) and System Organ Class (SOC), affected area, event start and end date (or ongoing), seriousness (yes/no), intensity, relationship to study product (yes/no), relationship to injection procedure (yes/no), UADE status, AESI status, action taken, outcome, time to onset, duration and Injection Timepoint. All AE endpoints will be presented Overall. The Overall Summary of Adverse Events table and the Adverse Events by System Organ Class and Preferred Term table will be presented Overall and by Injection Timepoint in which they occurred (see definition in [Section 4.5.2](#)). Additional presentations of AE endpoints may be presented by Injection Timepoint on an as needed basis.

Only AEs occurring after treatment will be included in analysis. AEs occurring before initial treatment, if any, will only be presented in data listings. Missing dates, intensity, relationship, and seriousness will be imputed as described in [Section 11.1](#) and [Section 11.2](#).

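### The two adverse-event tables split by injection timepoint use periods of unequal length and give no denominator for the touch-up column, so their columns cannot be read as first versus second injection

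*SAP*

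**What the plan says.** SAP 4.5.2 defines two periods for AE summaries. *Initial Treatment* runs "at or after Baseline injection until optional touch-up treatment or end of study (EOS), whichever comes first", and it adds: "All adverse events for subjects who did not receive optional touch-up treatment will be included in this injection timepoint". *Initial Treatment + Touch-up* runs from the touch-up to end of study and applies only to subjects who had one.

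The lengths follow from SAP 3.2, 4.2 (Table 6) and 4.3. "Optional touch-up treatment may be administered 1 month (4 weeks) after initial treatment", and the visit window adds up to 7 days. "Effectiveness and safety data will be collected for up to 12 months (48 weeks) after last treatment", the last visit has a window of 14 days either way, and a month is 28 days.

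Under SAP 10.2 all AE endpoints are shown Overall. The Overall Summary and the table by System Organ Class and Preferred Term (SOC/PT) "will be presented Overall and by Injection Timepoint in which they occurred"; other AE displays may be split this way as needed. SAP 10.2.1 specifies number and percentage of subjects and number of events. No subject-time rate, common window or per-period denominator is given.

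SAP 4.5.1 already has equal windows: 28 days after the Baseline injection and before touch-up, and "at or in the 28 days following optional Month 1 touch-up injection". The SAP's table of contents shows that this section serves the subject diary and exposure. AEs use 4.5.2 instead.

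**The concern.** A table with one column for the initial treatment and one for the touch-up invites the reader to compare them. Here the columns differ in observation time as well as in treatment, and the first mixes subjects observed for about four weeks with subjects observed for about 48. A crude percentage rises with time observed, so the columns can differ when the touch-up adds no risk.

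The second issue is between arms. The Treating Investigator and the subject decide on touch-up after randomization, and the Treating Investigator is not blinded (Protocol 5.6). Touch-up rates may therefore differ by arm. The arm with more touch-ups has less time in *Initial Treatment* and would show fewer subjects with AEs in that column for that reason alone.

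**Working it through.** **Period lengths (from the SAP).** Follow-up after last treatment is 12 × 28 = 336 days = 48 weeks, which reproduces the SAP's figure.

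| Subject | *Initial Treatment* | *Initial Treatment + Touch-up* |
|---|---|---|
| With touch-up | 28–35 days | 336 ± 14 days |
| Without touch-up | 336 ± 14 days | none |

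For a touched-up subject the second period is 336/35 = 9.6 to 336/28 = 12 times the first. Mean time in *Initial Treatment* at touch-up rate p is 4p + 48(1 − p) weeks: 34.8 at 30%, 26.0 at 50%, 17.2 at 70%.

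**Assumptions (not in the documents).** A constant AE rate λ unrelated to injection, the same in both arms and periods; touch-up rate p of 30% or 50%; touch-up at day 28.

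**Risk of at least one AE in d days:** 1 − exp(−λd/365.25).

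- λ = 0.5 per year: 3.76% over 28 days; 36.87% over 336 days.

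***Initial Treatment* column:** p × risk(28 d) + (1 − p) × risk(336 d).

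- p = 0.3: 0.3 × 3.76% + 0.7 × 36.87% = 26.9%
- p = 0.5: 0.5 × 3.76% + 0.5 × 36.87% = 20.3%

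**Touch-up column under the two possible denominators.**

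| Touch-up rate | *Initial Treatment* | Touch-up column, touched-up subjects | Touch-up column, all treated |
|---|---|---|---|
| 30% | 26.9% | 36.9% | 0.3 × 36.87% = 11.1% |
| 50% | 20.3% | 36.9% | 0.5 × 36.87% = 18.4% |

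With touched-up subjects as denominator the touch-up column looks 36.9/26.9 = 1.4 to 36.9/20.3 = 1.8 times riskier. With all treated subjects it looks less risky. No true difference was put in.

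**Arm gap in *Initial Treatment*, 30% against 50% touch-up.** 26.9% − 20.3% = 6.6 points. At λ = 1.0 per year the column shows 44.3% against 33.8%.

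**Second parameterization.** Set the background 48-week risk at 10–40%. At 30% against 60% touch-up the false gap is 2.7–10.7 points, or 2.5–9.7 points if each injection also carries a 10% risk of its own. At 20% against 70% it is 4.6–17.9 points without injection risk. With equal touch-up rates it is zero.

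**Overall column.** Observation is 48 weeks without and 52 weeks with touch-up. With background risk only, the gap is 0.2–0.8 points at 30% against 60%, and at most 1.3 points at 20% against 70%.

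**With 28-day windows.** At λ = 0.5 both columns show 3.8% in both arms, whatever the touch-up rate. With a 10% risk per injection and a background 48-week risk of 10–40%, both show the same 10.8–13.8%, and the false arm gap is zero.

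**The case against.** Several counter-arguments have weight.

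- **The main AE comparison is the Overall one.** This stands. Every AE endpoint is shown Overall, only two tables are committed to the split, and the SAP specifies no AE test between arms or periods.
- **The label signals cumulative treatment.** The periods can be read as assigning each AE to the treatment received so far, not as a first-against-second contrast. That is a fair reading of the intent, but side-by-side percentages will still be compared, and nothing tells the reader that observation time differs.
- **The sizes are assumed.** This stands. A constant rate unrelated to injection suits unrelated AEs best. For reactions that start soon after an injection the artefact shrinks towards zero, and the Overall Summary has separate rows for related and unrelated AEs. The unequal windows themselves are not an assumption.
- **Onset data help.** SAP 10.2.4 counts onset from the most recent treatment and lists related AEs that start after 21 days. This covers related AEs only and leaves the percentages unchanged.

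A reader might infer that these tables are the only safety evidence on the second injection. The documents do not support that. A diary is kept for 28 days after each treatment (Protocol Synopsis, Safety Assessments), pain is summarized before and after injection by visit (SAP 10.3), and acute visual-acuity change is summarized at injection visits (SAP 10.8.1).

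A reader might also divide 36.9% by 3.8% and report a roughly tenfold exaggeration of touch-up risk. No planned column shows that contrast, because *Initial Treatment* also contains the subjects without touch-up.

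**Conclusion.** The point holds for the by-timepoint columns of the Overall Summary and SOC/PT tables, and for any further table split the same way. Their periods are unequal by definition, the first column mixes short and long observation, and the denominator of the second is not stated. On the illustrative assumptions the columns differ by tens of percent in relative terms with no touch-up effect, in a direction set by the denominator. Touch-up rates of 30% against 50% give a false arm gap of about 6.6 points in *Initial Treatment*. These sizes rest on AE and touch-up rates that the documents do not supply.

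It would go too far to conclude that the safety comparison between arms is biased. The Overall columns are nearly unaffected by window length. If a touch-up carries its own injection risk, Overall will differ between arms with different touch-up rates, but that is a real consequence of more injections. This is a presentation defect in two descriptive tables, worth correcting because the remedy is cheap and already defined in the SAP.

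**What to change.** In SAP 4.5.2 and 10.2:

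1. Base the by-timepoint AE tables on the 28-day windows of 4.5.1. The first column takes AEs with onset within 28 days after the initial injection and before touch-up, over all treated subjects in the arm. The second takes onset within 28 days after touch-up, over touched-up subjects. State both denominators in the table.
2. Keep full follow-up in the Overall column. Say that AEs outside both windows, including those between day 28 and a touch-up given up to day 35, appear in Overall only.
3. If the long periods are kept, print subject-time and events per subject-month beside the percentages. This removes the artefact only if the AE rate is roughly constant, not if AEs cluster after injection.
4. In either case, footnote that touch-up recipients are a selected, non-randomized group. Equal windows do not isolate the effect of a touch-up.
5. Reconcile the cross-reference in 10.1, which sends exposure summaries to 4.5.2 although 4.5.1 is the exposure definition.

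The cost is SAP wording and a little table programming. The downside is that late-onset AEs leave the split tables; they remain in Overall, and related ones with onset after 21 days remain in the planned listing.
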